10.5.1. Summary of Association Analysis Results

The p-value for the main effect of genotype for each marker determined to be statistically significant will be listed in table format. The distribution of genotypes and the HWE p-value for corresponding analysis population will also be listed.

Markers determined to be statistically significant according to the criteria outlined in Section 7.6 will also be summarized graphically. Bar plots displaying the genotypes against case/control status for the significant markers will be produced.

Regional plots that depict patterns of association within each gene as well as the linkage disequilibrium among the SNPs in the gene will be produced if there are markers that meet the Tier-specific significance criteria.

The relationship between association patterns and annotated gene features can provide substantial insight into the robustness of association results. These plots will be generated using the statistical package R and/or other software.

11. INTERPRETATION AND REPORTING OF ASSOCIATION ANALYSES RESULTS

11.1. Focus on Strongest Exploratory Results

The raw p-values will be reported. P-value thresholds for significant or suggestive significant associations are defined in Section 7.6. The secondary analysis will be performed only on markers that passed the p-value threshold for suggestive evidence in the primary analysis. Any genetic markers that meet the significant p-value thresholds will be investigated carefully for biological context via 1) whether has supportive evidence from the secondary analysis; and 2) phenotypic distribution for the genotypes whether supports a plausible genetic model and the association. Markers having p-values which don't meet the significant threshold but pass the suggestive significant threshold may also be investigated for phenotypic distribution for the genotypes a plausible genetic model and the association. Genetic markers that show significance or suggestive significance will be reported and assessed for further investigation.

Beyond assessment of the p-values, the criteria that will be used to characterize the strength of support for a genetic association may include some of the following:

- Are the genetic effects consistent with commonly observed genetic models (i.e. dominant, partial dominant, additive, or recessive)?
- Are there a sufficient number of subjects in the risk genotype group driving the association to yield strong statistical support?
- Is there further genetic or biological evidence to support the statistically significant associations with diarrhea?
- Are there other statistically significant SNPs in LD with the associated SNPs?

12. **REFERENCES**

Abraham B, et al. Drug-induced Diahrrea. *Current Gsstroenterology Reports*. 2007;9:365.

Campbell CD, et al. Demonstrating stratification in a European American population. *Nature Genetics.* 2005;37:868.

Stein A, et al. Chemotherapy-induced diarrhea: pathophysiology, frequency and guideline-based management. *Ther Adv Med Oncol.* 2010;2:51.

Sternberg CN, et al. Pazopanib in locally advanced or metastatic renal cell carcinoma: results of a randomized phase III trial. *J Clin Oncol.* 2010;28:1061.

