2.2. Study Endpoints

The primary endpoint is the diarrhoea outcome status defined as:

- Case a patient who experienced a minimum of Grade 2 diarrhoea based on the National Cancer Institute Common Toxicity Criteria v3.0 (Table 2-1) during pazopanib treatment.
- **Control** a patient who received pazopanib for a minimum of 42 days, but never developed diarrhea. Forty-two days was the median time to first diarrhea event in patients treated with pazopanib in the studies.

Note that patients who experienced diarrhoea episodes at grade 1 are not included in the case-control analysis.

The secondary endpoint is diarrhoea toxicity grade levels from 1 to 5 (Table 2-1) and grade 0 for the control described above, defined as an ordinal categorical variable. As the number of subjects who experienced high diarrhoea toxicity grade (Grade 3+) is small, it may be possible to pool subjects with Grade 2-5 into a single category for the purposes of this analysis.

Grade	Description
1	Increase of <4 stools per day over baseline; mild increase in ostomy output compared
	to baseline
2	Increase of 4 – 6 stools per day over baseline; IV fluids indicated <24hrs; moderate
	increase in ostomy output compared to baseline; not interfering with activities of daily
	living
3	Increase of ≥7 stools per day over baseline; incontinence; IV fluids ≥24 hrs;
	hospitalization; severe increase in ostomy output compared to baseline; interfering
	with activities of daily living
4	Life-threatening consequences (e.g., hemodynamic collapse)
5	Death

Table 2-1 NCI's Common Toxicity Criteria v3.0 for Diarrhoea*

1. *Diarrhoea includes diarrhoea of small bowel or colonic origin, and/or ostomy diarrhoea.

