5.1. Retrospective Power Calculations

The power to detect a significant statistical genetic association is dependent upon several factors, such as the population prevalence of the event, the frequency of the risk genotype in cases, the size of the genetic effect, and the number of subjects analyzed. Basic retrospective power calculations were conducted to inform what kinds of genetic effects could be found given the observed numbers of diarrhoea cases in the clinical studies. These power calculations might be over-estimated given the assumption that no covariates are included in the model and that the causal variant itself will be assessed (as opposed to a variant in partial linkage disequilibrium with the causal variant).

Table 5-1 presents the subject count at each toxicity grade of diarrhoea in pazopanib treated ITT and PGx population. Power was calculated for diarrhoea case-control status, based on the expected number of RCC patients in pazopanib treated PGx population. The power was estimated assuming a 2 degree of freedom genotypic test conditional on the underlying genetic model being additive, dominant or recessive, respectively. These calculations assumed a type I error rate of 3.1×10^{-4} , the significance threshold with Bonferroni correction for Tier 1 markers (see Section 7.6 for the definition of Tier 1 markers). The plots show the relationship between statistical power and the odds ratio (OR) of the two homozygotes (Figure 5-1). The different curves correspond to power estimates assuming six different risk allele frequencies (RAFs).

Table 5-1	Summary of diarrhoea for pazopanib treated subjects in VEG102616,
	VEG105192 and VEG107769

Diarrhoea AE grade	ITT (%)	PGx population (%)			
0*	266 (45%)	156 (39%)			
1	202 (34%)	151 (38%)			
2	95 (16%)	78 (20%)			
≥3	21 (3.6%)	12 (3%)			
Missing data	2 (0.3%)	0			
Total	586	397			
1. * Without consideration of treatment time for pazopanib					

With 90 diarrhoea cases and 132 controls as defined in Section 2.2, there are many combinations of genotypic models, risk allele frequencies and odds ratios, that may lead to good statistical power (>80%) to detect an effect, especially if the dominant or additive models are true and if the risk allele is relatively common in the study population (i.e., MAF \geq 20% with a genetic effect OR \geq 4). The power to detect significant associations with SNPs from GWAS will be considerably reduced in comparison given approximately 1 million markers tests.

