10. GENETIC ANALYSIS

The Case-Control analyses will be performed on the binary outcome measure (diarrhoea status), using logistic regression analysis; the ordinal data analyses will be performed on ordinal categorical diarrhoea toxicity grade levels, using proportional odds model, if the marker meets the p-value threshold for suggestive evidence in the primary anlaysis. The analysis strategies that will be employed are outlined in this section.

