10.5. Evaluation of Genotypic Association

Logistic regression will be used to examine the effect of marker genotypes on the casecontrol status for diarrhoea (See Section 2.2 for diarrhoea case-control status definition). Prior to the PGx analysis, a model which includes necessary non-genetic independent variables that may influence the endpoints will be identified using the PGx Analysis Population (see Section 7.2 for the covariates that will be evaluated). The model may be reduced, if needed, to include only significantly predictive non-genetic terms (p<0.05) prior to beginning the genetic analyses. Multiple analyses will be run, evaluating each genetic marker, one at a time, while keeping covariates used constant throughout all analyses.

Proportional odds model, adjusting for some of the covariates, will be used to explore the effect of selected or all markers' genotypes on the ordinal diarrhoea toxicity grade levels if it is necessary. One hundred fifty one subjects classified as grade G1 diarrhoea toxicity level that are excluded in case-control analysis will be included in this analysis. The expected number of subjects in this analysis, by grade, is: 132 G0, 151 G1, and 90 G2-G4 (combined) subjects. The proportional odds assumption will be evaluated for the resulting three levels of diarrhoea toxicity. The analyses will be performed using ordinal logistic regression.

The following model will be fitted to identify the genetic effect.

Endpoint = PC1 + PC2 + ... PCn + Covariates + Genotype -- model (1)

The endpoint variables are those listed in Section 7.1. Covariates are those listed in Section 7.2. PC1 represents the first principal component based on the analysis of genome-wide markers, PC2 represents the second principal component and so on. The number of principal components necessary to characterize subject ancestry, n, will be analytically determined; for many datasets an n of 2 or 3 is adequate. An additive genetic model is used here. *Genotype* codes for the number of copies (0, 1, or 2) of the minor (less frequent) allele and will be evaluated as a numeric variable.

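### The ordinal analysis named in SAP Section 11.1 as the first check on a significant marker nearly repeats the primary test (null correlation 0.985) and adds almost no evidence

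*SAP*

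**What the plan says.** The primary analysis is a logistic regression of cases (Grade 2 or worse) against controls. SAP Section 5.1 gives its size: "With 90 diarrhoea cases and 132 controls as defined in Section 2.2". Section 2.2 states that "patients who experienced diarrhoea episodes at grade 1 are not included in the case-control analysis".

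The secondary analysis is a proportional odds model on the toxicity grade. Section 10 runs it "if the marker meets the p-value threshold for suggestive evidence in the primary anlaysis", and Section 11.1 repeats that restriction. Section 10.5 says that the Grade 1 subjects "that are excluded in case-control analysis will be included in this analysis", and gives the counts as "132 G0, 151 G1, and 90 G2-G4 (combined) subjects". One model statement serves both endpoints, with genotype as a 0/1/2 count: "An additive genetic model is used here".

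For a marker that meets its significance threshold, Section 11.1 lists two things to examine. The first is "whether has supportive evidence from the secondary analysis". The second is whether the phenotype distribution by genotype fits a plausible genetic model. The SAP does not say what level of ordinal result counts as supportive.

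**The concern.** A supporting analysis is useful to the extent that it can fail when the first result is a chance finding. Here the second analysis takes every patient from the first, keeps them as its two extreme categories, and is run only after the first has given a small p-value. If the added Grade 1 patients carry little weight, agreement is close to guaranteed whether or not the marker has any effect.

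What is at stake is how a significant marker is described. A reader of the genetic report who sees the hit supported by a second analysis will give it more credence than the data justify.

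**Working it through.** **Inputs.** Controls 132, Grade 1 151, Grade 2 and above 90, so N = 373 (Section 10.5). Cases 90 and controls 132, so n = 222 (Section 5.1); the 90 agrees with 78 + 12 in Table 5-1. Tier 1 has 53 markers, the candidate-gene set has 1380 in all, and Tier 3 has about 1 million (Sections 7.3.1 and 7.6).

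**The plan's own threshold.** (0.05/3)/53 = 3.14 × 10⁻⁴, which reproduces the 3.1 × 10⁻⁴ of Section 5.1; the two-sided z is 3.60. By the same rule Tier 2 is (0.05/3)/1327 = 1.26 × 10⁻⁵ and Tier 3 is (0.05/3)/10⁶ = 1.67 × 10⁻⁸.

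**Score weights for the genotype count, no covariates.**

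| Group | n | Case-control (a) | Proportional odds (b) = (number below − number above)/N |
|---|---|---|---|
| Control | 132 | −90/222 = −0.405 | −241/373 = −0.646 |
| Grade 1 | 151 | 0 | (132 − 90)/373 = +0.113 |
| Grade 2+ | 90 | +132/222 = +0.595 | +283/373 = +0.759 |

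**Null correlation.** r = Σnab / √(Σna² × Σnb²).

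- Σnab = 132 × 0.405 × 0.646 + 90 × 0.595 × 0.759 = 75.18
- Σna² = 53.51
- Σnb² = 108.83
- r = 75.18 / √(53.51 × 108.83) = 0.985

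Simulated null markers (400,000 at each of MAF 0.1, 0.2 and 0.4) gave 0.984 to 0.985. The Wald statistics from 600 pairs of fitted logistic and ordinal models gave 0.985. Keeping Grade 3+ as a fourth level (132/151/78/12) gives 0.982. Using all 156 Grade 0 patients gives 0.970, and both changes together give 0.968.

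**Chance of support for a null marker that passes the primary threshold.** Given a primary z, the ordinal z has mean r × z and SD √(1 − r²) = 0.172. At the Tier 1 cut-off the mean is 0.985 × 3.60 = 3.55. Averaging over the tail beyond each cut-off:

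| Primary threshold | Ordinal p≤0.05, same direction | Ordinal meets the same tier threshold |
|---|---|---|
| Tier 1, 3.14 × 10⁻⁴ | about 1.00 | 0.74 |
| Tier 2, 1.26 × 10⁻⁵ | about 1.00 | 0.69 |
| Tier 3, 1.67 × 10⁻⁸ | about 1.00 | 0.61 |

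An independent analysis would give 0.025 in the first column. Under a true proportional-odds effect (MAF 30%, per-allele OR 2), nominal support after a Tier 1 hit is also about 1.00, so at that level true and false hits are not separated.

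**Is an absent dose-response detected?** Suppose Grade 1 patients have exactly the control allele frequencies. The expected ordinal z is then (90 × 0.759/√108.83)/√53.51 = 6.55/7.32 = 0.895 times the expected primary z. For an expected primary z of 3.60 that is 3.22, still far beyond 1.96.

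**Grade 1 against controls alone.** Its null correlation with the primary test is √[(151 × 90)/(283 × 222)] = 0.465. At the Tier 1 cut-off the mean z is 0.465 × 3.60 = 1.68, with SD √(1 − 0.465²) = 0.885. Averaged over the tail, same-direction p≤0.05 occurs in about 42% of null Tier 1 hits. The same calculation gives about 80% at Tier 3. For a true per-allele OR of 2 at MAF 30%, about 80% of Tier 1 hits are supported.

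**The case against.** The SAP calls all its analyses exploratory and never describes the ordinal result as independent. Section 10.5 states openly that the Grade 1 patients are added to the others. Asking whether a hit survives their return is an ordinary sensitivity check, and such checks are expected to agree closely with the primary result. Section 11.1 also names a second check and several optional criteria, including outside genetic or biological evidence. All of this stands, and it limits the severity. It does not give the first check more information than the calculation shows.

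Three stronger readings are tempting, and the document does not support them.

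- A reader might infer that the ordinal result decides which markers go forward. Section 11.1 reports and assesses markers on the thresholds of Section 7.6, which are applied to the primary test.
- A reader might infer a raised false-positive rate. The primary thresholds are untouched by the secondary analysis.
- A reader might extend the argument to the suggestive markers, for example the 84% support given primary p≤0.05. Section 11.1 asks for ordinal support only for significant markers; for suggestive ones it mentions only the phenotype distribution.

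It is also fair that near-certain agreement depends on reading support as nominal significance. Under the strictest reading a null hit can fail, in 26% to 39% of cases.

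**Conclusion.** The point holds in limited form. On the SAP's own counts the ordinal statistic is almost the primary statistic again. With support read as same-direction p≤0.05, an assumption because no level is set, a false positive at any tier's threshold passes with probability about 1.00. With the tier threshold required a second time, the probability is 0.61 to 0.74.

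The calculation ignores covariates. Section 10.5 adjusts the ordinal model for only some of them, so a different covariate set could lower the correlation slightly. Other groupings of the grades or control counts leave it at 0.968 or above.

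The consequence is one of interpretation: the stated strength of support for a significant marker would rest partly on a check that carries almost no information. For an exploratory plan this is minor to moderate.

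**What to change.** In Section 11.1, replace item 1 with wording to this effect: the ordinal model is a sensitivity analysis that shares all primary subjects, and agreement with it is not independent corroboration.

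Add, for each significant marker, a per-allele logistic test of Grade 1 (151) against controls (132) with the primary model's covariates and principal components, as a dose-response check. State the level and direction that count as support. Record its limits beside it: it shares the controls, its null correlation with the primary test is 0.47, and the 42%, 80% and 80% figures derived above apply. It therefore discriminates somewhat at Tier 1. At Tier 3, nominal support means little because most null hits obtain it.

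A between-study heterogeneity test should not be used as the corroboration check. It is close to independent of the pooled effect. In a two-stratum simulation split 164/233 (VEG102616 against the other two studies, Table 3-1, assuming cases and controls split in the same way), it rejected at 0.05 in about 5% of null hits and about 5% of true hits. By-study estimates can be shown descriptively.

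The cost is a few sentences and one extra model run per reported significant marker, on existing data. The added contrast will be imprecise.

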13. APPENDIX

13.1. Diarrhoea PGx Candidate Gene List

Table 13-1 Diarrhoea PGx Candidate Gene List

Gene group	Gene Name	Gene region (NCBI36)	Functional Marker	Numbers of functional markers (Tier 1)	Numbers SNPs/gene (Tier 1 and 2)
Pazopanib's mode of action	FLT1	Chr13: 27,774,389-27,967,265	rs111458691	1	98
	KDR	Chr4: 55,639,406-55,686,519	rs2071559 rs2305948 rs1870377 rs34231037	4	41
	FLT4	Chr5: 179,961,112-180,009,230	rs307826	1	41
	PDGFRA	chr4:54,790,021-54,859,169	rs1800812	1	21
	PDGFRB	chr5:149,473,595-149,515,615			51
	KIT	chr4:55,218,852-55,301,638			55
	VEGFA	chr6:43,845,931-43,862,201	rs699947 rs833061 rs1570360 rs2010963 rs3025039	5	18
Pazopanib ADME	CYP3A4	chr7:99,192,540-99,219,744	rs2740574	1	38
	CYP3A5	chr7:99083749-99115557	rs776746	1	42
	CYP2C8	chr10:96,786,519-96,819,244	rs10509681 rs11572103 rs1058930	3	62
	NR112	chr3:120,984,247-121,020,022	rs3814055	1	83
	ABCB1	chr7:86,970,884-87,180,500	rs1128503 rs2032582 rs1045642	3	204
	ABCG2	Chr4:89,230,440-89,299,035	rs2231137 rs2231142 rs72552713	3	67

				-/	
	SLC6A4	chr17:25,549,032-25,586,841	rs25531 rs1042173	2	17
	IL10	chr1:205,007,571-205,012,462	rs1800896 rs1800872 rs1800871	3	14
	CFTR	chr7:116,907,253-117,095,954	rs73717525	1	50
	CLCA1	chr1:86,706,983-86,738,562			33
	SLC12A2	chr5:127,447,382-127,553,279			23
	ATP1A1	chr1:116,717,359-116,748,919			17
		abr2,24,005,542,24,005,550			27
l genes	ADCY3 ADCY6	chr12:24,895,542-24,995,559 chr12:47,446,242-47,464,144	rs3730071	1	30 9
	NOS3	chr7:150,319,080-150,342,609	RS2070744 RS1799983	2	21
	SLC9A3	chr5:526,425-577,447			31
	SLC5A1	chr22:30,769,259-30,836,645			27
	SLC26A3	chr7:107,193,148-107,230,914			22
ate		chr12:6 326 274 6 254 076	rs2228576	2	15
rel	SCNN1D	chr14,22,221,002,22,200,121	rc27E0224	Z	15
Diarrhoea	SCININIB		153759324		21
	SCNN1G	chr16:23,101,541-23,135,701			24
	ANO1	Chr11:69,602,294-69,713,282			57
	TNF	chr6:31,651,329-31,654,091	rs1800629 rs361525	2	28
	IFNG	chr12:66,834,817-66,839,788	rs2069727 rs2069707	2	12
	IL1B	chr2:113,303,808-113,310,827	RS16944 rs1143627	2	11
	IL4	chr5:132,037,272-132,046,267	rs2243250 rs2070874	2	18
	IL6	chr7:22,733,323-22,738,145	RS1800795 RS1800796 RS10499563	3	24
	IL8	chr4:74,825,139-74,828,297	rs4073 rs1126647	2	7
	IL12A IL12B	chr3:161,189,323-161,196,500 chr5:158,674,369-158,690,059	rs3212227 rs568408	2	12 12
	IL13	chr5:132,021,764-132,024,700	rs1881457 rs1800925 rs20541	3	12
Total				53	1380

 Table 13-2
 Diarrhoea PGx Candidate Gene List (continued)
